2 STUDY OBJECTIVES

2.1 Primary Objective

The primary objective is to evaluate the efficacy of deflazacort as measured by muscle function in subjects with Limb-Girdle Muscular Dystrophy Type 2I (LGMD2I).

2.2 Secondary Objectives

The secondary objectives are:

- To evaluate the effects of deflazacort on pulmonary function in subjects with LGMD2I.
- To evaluate the pharmacokinetic (PK) profile of deflazacort in subjects with LGMD2I.
- To evaluate safety of deflazacort in subjects with LGMD2I.

2.3 Exploratory Objectives

The exploratory objectives are

- To evaluate the predictive value of global T2 MRI as a measure of efficacy of deflazacort in subjects with LGMD2I.
- To evaluate quality of life by the Individualized Neuromuscular Quality of Life (INQoL) questionnaire in subjects with LGMD2I

3 ENDPOINTS

3.1 Primary Efficacy Endpoint

The primary efficacy endpoint is the change from baseline in time to climb 4 stairs for subjects with LGMD2I after 26 weeks of treatment for subjects who received at least one dose of deflazacort.

3.2 Secondary Efficacy Endpoints

The secondary endpoints are

- Change from baseline in forced vital capacity (FVC) after 26 weeks of treatment
- Change from baseline in 2-minute walk test after 26 weeks of treatment
- Change from baseline in time to up and go after 26 weeks of treatment

QMD Ref: Worldwide-TMP-ST-005-7.0 Effective: 12Aug2019	Governing QMD: Worldwide-SOP-ST-001
Confidentiality Statement	
This document is the property of Worldwide Clinical Trials Inc. and may not be duplicated, copied, altered or removed from company without prior approval from Worldwide Quality Assurance or in compliance with Worldwide Standard Operating Procedures.	

Worldwide Clinical Trials Controlled Quality Management Document		
 WORLDWIDE CLINICAL TRIALS	Sponsor:	PTC Therapeutics, Inc
	Protocol Number:	PTCEMF-GD-004
STATISTICAL ANALYSIS PLAN		

- Change from baseline to time to descent 4 stairs after 26 weeks of treatment
- Change from baseline in time to run/walk 10 meters after 26 weeks of treatment
- Change from baseline in maximal inspiratory pressure (MIP) and maximal expiratory pressure (MEP) after 26 weeks of treatment
- Change from baseline in hand-held myometry after 26 weeks of treatment
- Change from baseline in global T2 relaxation time of selected upper and lower limb muscles after 26 weeks of treatment

3.3 Exploratory Efficacy Endpoints

- Change from baseline in muscular fat using Dixon magnetic resonance imaging of selected lower limb muscles after 26 weeks of treatment
- Change from baseline in the INQoL questionnaire in subjects with LGMD2I after 26 weeks of treatment

3.4 Safety Endpoints

Safety profile characterized by type frequency, severity, timing, and relationship to study drug of any adverse events, laboratory abnormalities, electrocardiogram (ECG) abnormalities, ophthalmologic abnormalities, dual-energy X-ray absorptiometry (DEXA) to evaluate bone density and/ or X-ray to assess spine fracture.

3.5 Pharmacokinetic Endpoints

Pharmacokinetic assessments at baseline and after 13 weeks of treatment. PK analyses will be discussed in a separate SAP.

4 SAMPLE SIZE

This is a single arm, open label study to evaluate the efficacy and safety of deflazacort in subjects with LGMD2I. The primary endpoint is the change in 4-stair climb in seconds after 26 weeks of treatment.

Sample size is based on assuming the deflazacort can prevent subjects' further progression within 6 months i.e. the mean change of 4-stair climb after 26 weeks of treatment is 0 second and the standard deviation of the change is 0.7, with a total of 30 subjects, the 95% confidence will be from -0.25 to 0.25 seconds.

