## **9 STATISTICAL CONSIDERATIONS**

### **9.1 Statistical Hypothesis**

No hypothesis will be tested in this study.

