This document is the property of Worldwide Clinical Trials Inc. and may not be duplicated, copied, altered or removed from company without prior approval from Worldwide Quality Assurance or in compliance with Worldwide Standard Operating Procedures.	

Worldwide Clinical Trials Controlled Quality Management Document

Sponsor: PTC Therapeutics, Inc

Protocol Number: PTCEMF-GD-004

STATISTICAL ANALYSIS PLAN

Subjects Randomized to Placebo Prior to 01 February 2020	Subjects will have the option to be consented under Version 4.0 and immediately accelerated to the Week 26 visit and begin the open label study.
Subjects Randomized to Deflazacort Prior to 01 February 2020	Subjects will return to the clinic at their scheduled Week 26 Visit under Version 3.0. At the Week 26 visit, the subject will undergo Week 26 procedures and have the option to re-consent under Protocol Version 4.0 and continue for an additional 26 weeks in the open label period.
Subjects Randomized to Placebo AFTER 01 February 2020	Subjects will have the option to be consented under Protocol Version 4.0 and begin at the Week 26 Visit (Open-label period).
Subjects Randomized to Deflazacort AFTER 01 February 2020	Subjects will have the option to be consented under Protocol Version 4.0 at their Week 13 Visit. These subjects will be provided the option to re-consent to the study under Protocol Version 4.0 at Week 13 and continue until Week 26. After Week 26, the subjects will be ineligible to continue for the additional 26 weeks of open label treatment.
New subjects enrolled until 31 May 2020	Subjects will have the option to be consented under Protocol Version 4.0 and perform Baseline through Week 26 visit procedures. These subjects will be assigned deflazacort in an open-label fashion. After Week 26, the subjects will be ineligible for the additional 26 weeks of the trial.

On 23rd July 2020, a PTC corporate decision was made to terminate the study early due to the slow recruitment and company’s strategy change. This decision is not related to the safety or efficacy of the study drug. Due to the early termination, only 11 subjects were enrolled in this study.

QMD Ref: Worldwide-TMP-ST-005-7.0 Effective: 12Aug2019

Governing QMD: Worldwide-SOP-ST-001

Confidentiality Statement

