6.3 Conventions

All data listings, summaries, figures, and statistical analyses will be generated using SAS version 9.4 or higher¹.

Summary displays based on the Enrolled Population will have Overall as the column header. In all summary tables, all subjects who received at least one dose of deflazacort will be pooled regardless of the protocol versions they were enrolled, and the treatment column will be displayed as Deflazacort. Deflazacort treated subjects will be pooled in all safety summaries across all deflazacort treated periods.

The following defined study period will be presented in the by-subject listings only:

- Placebo period: The observations before entering to open label for subjects randomized to placebo under protocol version 3.0.

Listings will be sorted in the following order parameter, subject and visit (sorted in chronological order – earliest to latest) unless otherwise stated. The appropriate study period will be included in the listings.

Continuous variables will be summarized by the number of non-missing observations, mean, median, standard deviation, and minimum and maximum. For the primary and secondary efficacy endpoints, the lower and upper 95% confidence limits for the mean will be provided.

QMD Ref: Worldwide-TMP-ST-005-7.0 Effective: 12Aug2019	Governing QMD: Worldwide-SOP-ST-001
Confidentiality Statement	
This document is the property of Worldwide Clinical Trials Inc. and may not be duplicated, copied, altered or removed from company without prior approval from Worldwide Quality Assurance or in compliance with Worldwide Standard Operating Procedures.	

Worldwide Clinical Trials Controlled Quality Management Document		
 WORLDWIDE CLINICAL TRIALS	Sponsor:	PTC Therapeutics, Inc
	Protocol Number:	PTCEMF-GD-004
STATISTICAL ANALYSIS PLAN		

Categorical variables will be summarized by percentage and frequency counts. Percentages will be based on the number of non-missing observations or the subject population unless otherwise specified. For each variable, all categories will be shown.

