6.10.1 Analysis of Primary Endpoint

The actual value and the change from baseline in 4-stair climb time, measured in seconds will be summarized descriptively (number of non-missing observations (n), mean, standard deviation, minimum, median, and maximum) at each assessment visit for the Full Population. The time to climb 4 stairs is performed twice at each visit. The maximum value at each visit will be used for summary and analysis purposes.

In addition, the 95% confidence interval for the mean change from baseline after 26 weeks of deflazacort treatment will be provided.

A waterfall plot of the change in 4- stair climb time at Week 26 will be provided.

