9 CHANGES TO PLANNED PROTOCOL ANALYSIS

Due to the early termination of the study (decision made 23rd July 2020), only 11 subjects were enrolled in the study with limited information. Medical History, Concomitant medications, Exploratory Efficacy Endpoints (except fat fraction), Laboratory results, Vital Signs, ECG, Physical Examination and Ophthalmology examination information will be presented only in listings instead of summary tables. In addition, Dixon MRI and T2 MRI endpoints is not collected and will not be summarized or listed.

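### Does SAP Section 4 need correcting because it still gives ±0.25 s for 30 subjects when only 11 were enrolled?

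*SAP*

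**What the plan says.** SAP Section 4 repeats the precision statement of Protocol Section 9.2. It assumes a mean change of zero after 26 weeks and that "the standard deviation of the change is 0.7", and concludes that "with a total of 30 subjects, the 95% confidence will be from -0.25 to 0.25 seconds". The passage is introduced as the assumption on which the sample size rests.

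SAP Section 1 reports the decision of 23 July 2020 to terminate, with its reasons, and adds: "Due to the early termination, only 11 subjects were enrolled in this study". Section 9, on changes to the planned analysis, repeats that "only 11 subjects were enrolled in the study with limited information" and moves several displays from summary tables to listings. It does not mention the precision of the primary endpoint.

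The primary analysis is kept. Under SAP Section 6.10.1, "the 95% confidence interval for the mean change from baseline after 26 weeks of deflazacort treatment will be provided", along with the number of observations, mean, SD, median, minimum and maximum, and a waterfall plot. SAP Section 6.3 says of the primary and secondary efficacy endpoints that "the lower and upper 95% confidence limits for the mean will be provided". Neither section names the quantile. Protocol Section 9.1 states: "No hypothesis will be tested in this study".

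**The concern.** The SAP's electronic signatures are dated 4 November 2020, more than three months after the termination decision, so its authors knew the enrolment when they approved Section 4. Even so, that section carries the 30-subject width without marking it as superseded, and no other section gives the width to expect from 11. With no hypothesis test there is no power statement, so the expected interval width is the only measure of performance the design offers for its primary endpoint. A reader of Section 4 alone could expect an estimate far more precise than 11 subjects can give.

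The missing quantile adds to this. The one worked figure, ±0.25 s, comes from the normal quantile. If the reported interval were built in the same way from about ten subjects, it would be too narrow and would cover the true mean less often than 95% of the time.

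**Working it through.** **Inputs.** SD of change 0.7 s, planned n = 30 and stated half-width 0.25 s (SAP Section 4, Protocol Section 9.2); enrolled n = 11 (SAP Sections 1 and 9). The number with a Week 26 value is not given. It cannot exceed 11, and the rows below 11 are assumptions.

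**Formulas.** Half-width = 1.96 × SD / √n (normal) or t(0.975, n−1) × SD / √n (t).

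**The plan's own figure.** 1.96 × 0.7 / √30 = 0.2505 s, which reproduces ±0.25 s. Inverted, (1.96 × 0.7 / 0.25)² = 30.1 subjects. With t the result is 2.045 × 0.7 / √30 = 0.2614 s.

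**Other numbers of subjects, SD 0.7 s:**

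| n | normal (s) | t quantile | t (s) |
|---|---|---|---|
| 30 (planned) | 0.2505 | 2.045 | 0.2614 |
| 11 (enrolled) | 0.4137 | 2.228 | 0.4703 |
| 10 (assumed) | 0.4339 | 2.262 | 0.5007 |
| 9 (assumed) | 0.4573 | 2.306 | 0.5381 |
| 8 (assumed) | 0.4851 | 2.365 | 0.5852 |

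**Ratios of n = 11 to n = 30.** 0.4137 / 0.2505 = 1.65 (normal); 0.4703 / 0.2614 = 1.80 (t).

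**SD that would keep ±0.25 s at n = 11.** 0.25 × √11 / 1.96 = 0.42 s (normal); 0.25 × √11 / 2.228 = 0.37 s (t).

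**Effect of the quantile.** The half-widths differ by 0.2614 − 0.2505 = 0.01 s at n = 30 and by 0.4703 − 0.4137 = 0.06 s at n = 11. For normally distributed changes, an interval of mean ± 1.96 × s / √n covers 1 − 2 × P(T with n−1 df > 1.96): 94.0% at n = 30, 92.2% at n = 11 and 90.9% at n = 8.

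**What uses the figure.** Nothing later in the plan does:

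- Enrolment is over, so the figure cannot change the number of subjects.
- No hypothesis is tested, no interim analysis is planned (SAP Section 7), and neither document sets a success threshold or a limit on interval width.
- The interval in SAP Section 6.10.1 is computed from the observed changes. Neither the 0.7 s nor the 30 enters it.

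**The case for a change.** The strongest case for a change is that a plan approved after termination should not leave its only precision statement looking current. Section 9 exists to record what termination altered, yet it is silent on the primary endpoint. Saying that ±0.25 s no longer applies, giving the width for 11 and naming the t interval would take a few sentences and no new analysis.

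The arithmetic behind this stands, and so do the two omissions: no section gives a width for 11 subjects, and none names the quantile. What does not stand is that either omission harms the trial's results.

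The Section 4 statement is conditional on 30 subjects and on the assumed SD, and it remains true. Section 9 lists changes to analyses, and the primary analysis did not change. Replacement half-widths would reuse the planning SD, for which the documents give no source, together with a Week 26 number they do not report. The observed interval, shown with its n and SD, will convey the imprecision better than such a projection.

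The coverage loss describes an interval that the SAP does not prescribe. The normal quantile is inferred only from a rounded planning figure; Sections 6.3 and 6.10.1 do not adopt it. An analyst computing confidence limits for a mean from 11 or fewer subjects, with the SD estimated from the same data, would be expected to use t.

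**Conclusion.** No change is needed. The ±0.25 s is a correct planning figure that enrolment overtook. The SAP says openly, in two places, that 11 subjects were enrolled. At the planning SD the interval would be about ±0.47 s with t, some 1.8 times the t-based width for 30 subjects, and wider if fewer than 11 have Week 26 data. That loss of precision comes from the early termination, and rewording Section 4 would not recover any of it.

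The unnamed quantile is a gap that analysts fill sensibly, worth 0.06 s in half-width at 11 subjects and the planning SD. A cross-reference from Section 4 to Section 9 would be tidy, but it would alter no analysis, result or decision.

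This conclusion rests on three things: the interval will be calculated from the observed data by the usual t method, it will be reported with its n and SD as Section 6.10.1 provides, and nothing in the plan turns on its width. The half-widths for 11 and fewer assume an SD of 0.7 s; the observed SD could make the interval narrower or wider.

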5 RANDOMIZATION

QMD Ref: Worldwide-TMP-ST-005-7.0 Effective: 12Aug2019	Governing QMD: Worldwide-SOP-ST-001
Confidentiality Statement	
This document is the property of Worldwide Clinical Trials Inc. and may not be duplicated, copied, altered or removed from company without prior approval from Worldwide Quality Assurance or in compliance with Worldwide Standard Operating Procedures.	

Worldwide Clinical Trials Controlled Quality Management Document		
 WORLDWIDE CLINICAL TRIALS	Sponsor:	PTC Therapeutics, Inc
	Protocol Number:	PTCEMF-GD-004
STATISTICAL ANALYSIS PLAN		

Subjects enrolled under protocol v3.0 were 1:1 randomized to get placebo or deflazacort. After protocol v4.0, the study became an open label study and all subjects received deflazacort.

6 STATISTICAL ANALYSES

Subjects will be pooled in all efficacy and safety analyses regardless of the protocol version they enrolled. No summary tables will be provided for the events or assessments occurred during the placebo period for subjects who enrolled prior to protocol version 4.0 and randomized to placebo group. All events or assessments occurred during the placebo period will be presented in the by-subject listings only.

Subjects who took at least one dose of deflazacort will be pooled in the safety and efficacy summaries. Safety and efficacy listings will be provided including the events and measurements occurred during placebo period.

6.1 Analysis Populations

Subjects excluded from the analysis sets and the reason for their exclusion will be presented in the by-subject listings only.

6.1.1 Enrolled Population

The Enrolled population includes all informed-consented subjects who meet all inclusion and exclusion criteria.

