### **9.3 Population for Analyses**

#### **9.3.1 Full/Safety Population**

The Full/Safety population includes all enrolled subjects who receive at least one dose of deflazacort.

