6.1.2 Full / Safety Population

The Full and Safety Populations consist of all enrolled subjects who received at least one dose of deflazacort.

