6.4 Subject Disposition

Subject disposition will be summarized as follows:

- The number of subjects, who entered the study under protocol v3.0, who entered the study under protocol v4.0, who entered the open label, were randomized under protocol v3.0, who were transitioned to the open label by previous treatment received and overall, who received at least 1 dose of study drug and who are in each analysis set will be summarized for the Enrolled Population.
- The number of subjects screened, and the number of subjects who had screening failed. The number of subjects who prematurely discontinued study drug and the discontinuation reason will be tabulated for the Safety Population.

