6.9 Exposure to Study Drug

Deflazacort treatment duration (days) is defined as the date of last deflazacort dose before tapering – the date of first deflazacort dose +1. The deflazacort treatment duration will not consider breaks in therapy.

Exposure will be summarized in all deflazacort treated subjects across all deflazacort treated periods using Safety Population.

Placebo treatment duration (days) is defined as the date of last placebo dose – the date of first placebo dose +1. Placebo treatment duration will only be presented in the by-subject listings.

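### Read together, SAP 6.1.1 and 6.1.2 could leave a dosed subject with an eligibility breach out of the Full/Safety Population, against the dose-only rule used elsewhere in the SAP

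*SAP*

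**What the plan says.** The SAP defines its populations in sequence. Section 6.1.1: "The Enrolled population includes all informed-consented subjects who meet all inclusion and exclusion criteria". Section 6.1.2, directly after it: "The Full and Safety Populations consist of all enrolled subjects who received at least one dose of deflazacort". Section 6.1.3 starts the PK population from enrolled subjects in the same way.

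Elsewhere the SAP describes the analysed subjects by dosing:

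- Section 3.1 sets the primary endpoint "for subjects who received at least one dose of deflazacort".
- Section 6: "Subjects who took at least one dose of deflazacort will be pooled in the safety and efficacy summaries".
- Section 6.3: "In all summary tables, all subjects who received at least one dose of deflazacort will be pooled regardless of the protocol versions".
- Section 6.9: "Exposure will be summarized in all deflazacort treated subjects across all deflazacort treated periods using Safety Population".

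Protocol 9.3.1 reads much like SAP 6.1.2: "The Full/Safety population includes all enrolled subjects who receive at least one dose of deflazacort". The protocol, however, has no population defined by eligibility. Protocol 3.1 treats enrolment as something that happens at Visit 1 to subjects who have passed screening.

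**The concern.** Section 6.1.1 is the only definition of enrolled in the SAP, and it makes full eligibility a condition. Carried into 6.1.2, it makes the Full/Safety Population consented, fully eligible and dosed. A subject dosed in error despite failing a criterion would then be outside both populations, and no SAP sentence says that such a subject stays in.

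The case is foreseeable. Protocol 10.1.8 puts failure to adhere to the eligibility criteria first among its examples of deviations. The same section prohibits waivers, so a breach could arise only by error, but a safety population should still include someone dosed in error.

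At stake is whether that subject's adverse events and efficacy values reach the summary tables or only the listings. With 11 subjects enrolled (SAP 1), one subject is a visible share of any table.

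**Working it through.** **The two rules side by side**

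- Rule A (6.1.2 with the 6.1.1 meaning): consented, and all criteria met, and at least one deflazacort dose.
- Rule B (SAP 3.1, 6, 6.3): at least one deflazacort dose.
- Section 6.9 names all treated subjects and the Safety Population for the same summary, so it takes the two groups to be identical. That is true under Rule B. Under Rule A it is true only if nobody dosed was ineligible.

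For subjects who consented, A and B differ by exactly the dosed subjects with an eligibility breach. If there are none, the two sets are the same.

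**The plan's own precision figure**

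Inputs from SAP 4: n = 30, SD of change 0.7 s, mean change 0, 95% interval stated as -0.25 to 0.25 s.

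- Normal half-width: 1.960 × 0.7/√30 = 0.2505 s, which reproduces the stated 0.25 s.
- With the t distribution at n = 30 the half-width is 0.261 s.

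Choosing Rule A or Rule B changes no planned figure.

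**Illustration at the actual size**

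Inputs: 11 enrolled (SAP 1) and SD 0.7 s (SAP 4). Assumptions that the documents do not establish: all 11 received deflazacort and, for the half-width only, all 11 have Week 26 data. Half-width = t(0.975, n−1) × 0.7/√n.

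| Dosed subjects dropped | n | Share of 11 | Half-width |
|---|---|---|---|
| 0 | 11 | 0% | 2.228 × 0.2111 = 0.470 s |
| 1 | 10 | 1/11 = 9.1% | 2.262 × 0.2214 = 0.501 s |
| 2 | 9 | 2/11 = 18.2% | 0.538 s |

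The number of dosed subjects with a breach is not in the documents; 0 to 2 is an assumed range.

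For an adverse event seen in one subject only, if that subject is the one dropped:

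- Rule B: 1/11 = 9.1%, exact (Clopper-Pearson) 95% CI 0.2% to 41.3%.
- Rule A: 0/10 = 0%, exact 95% CI 0% to 30.8%.

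**Where eligibility itself is unclear**

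Inclusion criterion 3 (Protocol Synopsis and 4.2) gives a lower limit of 2.5 s for the 4-stair ascent and no upper limit. Footnote 12 of the Schedule of Events (Protocol Table 6, repeated in SAP Figure 1) gives 2.5 s and an upper limit of 8 s. For a subject slower than 8 s, whether all criteria are met depends on which passage is applied.

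**The case against.** The best reply is that Rule A is not what the authors meant, and much of that reply stands. Section 6.1.2 does not refer to the Enrolled Population by name. It uses the lower-case word, which elsewhere in the SAP means entry to the study, as in the count of 11 in Section 1. The wording of 6.1.1 looks like shorthand for passing screening. Sections 6 and 6.3 already say who is tabulated, although the stress in 6.3 is on pooling across protocol versions and neither section mentions eligibility breaches. What remains is that the only definition of enrolled carries an eligibility condition, and nothing in the SAP sets it aside for 6.1.2.

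It is also fair that nothing would be hidden. SAP 6.1 requires subjects excluded from an analysis set to be listed with the reason, and 6.5 lists protocol deviations. This limits the harm to the summary tables.

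The illustration rests on stacked assumptions. Screening could run to 31 May 2020 (Protocol 3.4) and the decision to stop came on 23 July 2020 (SAP 1), so complete Week 26 data cannot be presumed. Nor can deflazacort dosing of all 11, since some subjects may have been randomised to placebo and not transitioned. The study tests no hypothesis (Protocol 9.1), and the change in half-width is small.

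A reader might also infer from SAP 6.4 that 6.1.1 would make the dosed count in the disposition table disagree with the Safety N. That section counts subjects "who received at least 1 dose of study drug and who are in each analysis set will be summarized for the Enrolled Population". The inference does not hold as a consequence of 6.1.1. Study drug in the SAP includes placebo, whereas Safety requires deflazacort, so the two counts can differ whatever 6.1.1 says.

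**Conclusion.** The point holds as a minor wording conflict. The SAP's only definition of enrolled, applied to 6.1.2, can remove a dosed subject with an eligibility breach from the summary tables, while 3.1, 6 and 6.3 would keep that subject and 6.9 assumes that the two groups coincide. Dose-only is the likelier intent.

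The effect is zero unless an ineligible subject was dosed. The shift from 0.47 s to 0.50 s and the drop from 1/11 to 0/10 show scale only, under the assumptions given with them. Confidence is medium, because the conflict depends on how one word in 6.1.2 is read.

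A reader might go further and infer that a treated subject was in fact excluded, or that the clash between criterion 3 and footnote 12 shows someone was ineligible. The documents support neither. The clash shows only one way in which the 6.1.1 condition could come into play.

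**What to change.** - **SAP 6.1.2:** define Full/Safety as all subjects who received at least one dose of deflazacort, regardless of eligibility deviations.
- **SAP 6.1.1:** define Enrolled by the act of enrolment at Visit 1, without an eligibility condition.
- **SAP 6.1.3:** word it to match, for consistency only; no conflict in the PK analysis is claimed.
- **Separately:** the sponsor should reconcile inclusion criterion 3 with Schedule of Events footnote 12 in both documents. No view is taken here on which is right.

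The cost is two SAP sentences, one matching edit and a separate reconciliation of the eligibility wording. No new data are needed and no planned figure changes.
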